## Section 11 – Medical Therapy

- ! Antibiotic prophylaxis (Yes/No)
- ! Antifungal prophylaxis (Yes/No)
- ! Use of somatostatin analogs (Yes/No)
- ! Nutritional support on admission (Oral/Enteral via nasogastric feeding tube/Enteral via nasojejunal feeding tube/Total parental nutrition/Nihil per os)

Section 12 – Cholecystectomy (Yes-within 3 days/Yes-within 7 days/Yes-within 14 days/No-delayed cholecystectomy)

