#### The rationale for the study

Despite existing evidence-based practice guidelines for the management of biliary AP, in Europe, clinical compliance with recommendations is lacking. Studies in this field have identified significant discrepancies between evidence-based recommendations and daily clinical practice.

It is believed by many that clinical guidelines would help to decrease inappropriate variation in practice, that they provide a rational basis for referral, and that they would help to reduce uncertainty in the management of some conditions. Clinical guidelines also provide a basis for continuing medical education and can improve control of healthcare costs. However, the value of national and/or international guidelines is very much dependent on a strategy for their implementation. Although different guidelines for the management of biliary AP have been published, they have not been adequately investigated, and compliance has generally been unsatisfactory. Deficiencies and lack of standardization of the management of AP worldwide have been reported.

The most commonly reported gaps between clinical practice and AP guidelines include the indications for CT scan, need and timing of artificial nutritional support, indications for antibiotics, and surgical/endoscopic management of biliary AP.

The MANCTRA-1 can identify a number of areas for quality improvement that will require new implementation strategies. We aim to summarize the main areas of sub-optimal care due to the lack of compliance with current guidelines to provide the basis for introducing a number of bundles in AP patients' management to be implemented during the next years.

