#### Primary objective

! To evaluate which items of the current AP guidelines, if disregarded, correlate with

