#### Secondary outcomes

- ! Early definitive treatment rate in 2019 vs. 2020: defined as treatment in accordance with the current guidelines (cholecystectomy or ERCP with endoscopic sphincterotomy during the same hospital admission or within 2 weeks of discharge)
- ! 30-day hospital readmission rate in 2019 vs. 2020: defined as hospital readmission within 30days from discharge for recurrent biliary AP while awaiting interval cholecystectomy, or due to post-cholecystectomy complications
- ! Predictive factors of morbidity and mortality in patients with biliary AP

The compliance of surgeons to the most up-to-date international guidelines on biliary AP will be assessed through the analysis of the following attitudes:

! Use of scoring systems for the diagnosis and severity grading of biliary AP

- ! Use of lipase dosage (for the diagnosis) and CRP (for the severity grading) during the diagnostic workup
- ! Use of Ultrasound scan, CT scan, MRCP, and endoscopic Ultrasound scan (EUS) in the correct way and timing
- ! Use of early ERCP and sphincterotomy in case of cholangitis and/or choledocholithiasis
- ! Use of percutaneous and/or endoscopic drainage in case of infected pseudocyst or necrosis
- ! Timing of surgical necrosectomy
- ! Timing of re-laparotomy in case of open abdomen strategies
- ! Use of prophylactic antibiotics/antifungals
- ! Use of somatostatin analogs
- ! Use of early enteral feeding
- ! Use of early definitive treatment strategies, including cholecystectomy and/or ERCP and sphincterotomy

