#### Section 7 – Diagnostic Imaging

! Initial diagnostic imaging (Ultrasound scan on admission/CT scan on admission/CT scan <24h/CT scan 24-48h/CT scan >48h)

- ! MRCP (MRCP on admission/MRCP <24h/MRCP >24h/No)
- ! Endoscopic ultrasound scan (Yes <24 hours/Yes >24 hours/No)
- ! Re-evaluation with CT scan (None/<7 days/7-14 days/15-30 days/>30 days)

Section 8 – Physical examination on admission (Localized abdominal pain/Localized abdominal rigidity/Diffuse abdominal pain/Diffuse abdominal rigidity/No abdominal pain/No abdominal rigidity)

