## Table\_3. Statements and Recommendations from the 2018 American Gastroenterological

Association Institute Guideline on Initial Management of Acute Pancreatitis.

1.	!	Recommendation 1A. In patients with AP, the AGA suggests using goal-directed therapy for fluid management. Conditional recommendation, very low quality evidence. Comment: The AGA makes no recommendation whether normal saline or Ringer's lactate is used.
	!	Recommendation 1B. In patients with AP, the AGA suggests against the use of hydroxyethyl starch (HES) fluids. Conditional recommendation, very low quality evidence.
2.	!	Recommendation 2. In patients with predicted severe AP and necrotizing pancreatitis, the AGA suggests against the use of prophylactic antibiotics. Conditional recommendation, low quality evidence.
3.	!	Recommendation 3. In patients with acute biliary pancreatitis and no cholangitis, the AGA suggests against the routine use of urgent ERCP. Conditional recommendation, low quality evidence.
4.	!	Recommendation 4. In patients with AP, the AGA recommends early (within 24 hours) oral feeding as tolerated rather than keeping the patient nil per os. Strong recommendation; moderate quality evidence.
5.	!	Recommendation 5. In patients with AP and inability to feed orally, the AGA recommends enteral rather than parenteral nutrition. Strong recommendation, moderate quality evidence.
6.	!	Recommendation 6. In patients with predicted severe or necrotizing pancreatitis requiring enteral tube feeding, the AGA suggests either nasogastric or nasoenteral route. Conditional recommendation, low quality evidence.
7.	!	Recommendation 7. In patients with acute biliary pancreatitis, the AGA recommends cholecystectomy during the initial admission rather than after discharge. Strong recommendation, moderate quality evidence.

From: Crockett SD, Wani S, Gardner TB, Falck-Ytter Y, Barkun AN; American Gastroenterological Association Institute Clinical Guidelines Committee. American Gastroenterological Association Institute Guideline on Initial Management of Acute Pancreatitis. Gastroenterology. 2018 Mar;154(4):1096-1101. doi: 10.1053/j.gastro.2018.01.032. Epub 2018 Feb 3. PMID: 29409760.

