10. Protease inhibitor	! The effectiveness of intravenous administration of protease inhibitor (gabexate mesilate) for improving the life prognosis and the rate of complications of acute pancreatitis has not been clearly proven. Further consideration of the efficacy of continuous high-dose intravenous administration for severe cases is required. (ungraded B)
11. Nutritional support	
 
! Intravenous hyperalimentation is not recommended for mild cases. (1B)
 
! Total parenteral nutrition (not performed with oral or enteral nutrition) should be avoided if possible. (1B)
 
! In severe cases, it is more significant as a measure to prevent infection rather than as a route of nutrition support. It can be applied and implemented for severe cases which do not have accompanying intestinal complications. (1A)
 
! If initiated in the early phase, enteral nutrition can reduce the incidence of complications and can contribute to an increased rate of survival. Therefore, it is desirable that it be started within at least 48 h of admission. (2A)
 

	
 
! In principle, it is recommended that enteral feeding tubes be inserted into the jejunum through the Treitz ligament. However, if a feeding tube cannot be inserted into the jejunum, nutrients can be infused into the duodenum or stomach instead. (2B)
 
! The initiation of oral administration should be determined using indicators such as the subsidence of abdominal pain and the serum pancreatic enzyme (especially serum lipase) level, etc. (2B)
 

12. Intensive care	
 
No life-saving effect has been observed from peritoneal lavage for acute pancreatitis, and therefore it is not recommended. (2B)
 
For severe cases where circulation dynamics are not stable with anuria even after sufficient initial fluid infusion or cases with abdominal compartment syndrome (ACS), CHF/CHDF should be introduced. (1C)
 
The efficacy of CHF/CHDF in cases of severe acute pancreatitis not mentioned above is uncertain. Therefore, routine use is not recommended. (2C)
 
Continuous Regional Arterial Infusion therapy is reported to be effective in reducing pancreatic infection and mortality rates for severe acute pancreatitis and acute necrotizing pancreatitis, but its efficacy has not been confirmed. (ungraded B)
 

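### Early enteral feeding is a compliance item, but the CRF records only the route of nutrition on admission and no start time, so earliness cannot be scored

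*Combined protocol and SAP*

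**What the plan says.** - **Compliance item.** Secondary outcomes lists eleven attitudes by which compliance will be judged. One is "Use of early enteral feeding". The plan does not define early, and does not say whether oral feeding counts.
- **Primary objective.** The study sets out "To evaluate which items of the current AP guidelines, if disregarded, correlate with" negative outcomes, so the same item also serves as an exposure.
- **Rationale.** Among the most commonly reported gaps in practice, the rationale names "need and timing of artificial nutritional support".
- **CRF Section 11 (Medical Therapy).** The nutrition field reads "Nutritional support on admission (Oral/Enteral via nasogastric feeding tube/Enteral via nasojejunal feeding tube/Total parental nutrition/Nihil per os". No other CRF section asks about feeding.
- **Table 3, recommendation 4.** "the AGA recommends early (within 24 hours) oral feeding as tolerated rather than keeping the patient nil per os". No starting point for the 24 hours is named.
- **Table 4, item 11.** For enteral nutrition, "it is desirable that it be started within at least 48 h of admission".
- **CRF Section 7.** For another item, the form offers "MRCP (MRCP on admission/MRCP <24h/MRCP >24h/No", so arrival and the first 24 hours are separate answers.

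Neither the Statistical analysis section nor the CRF gives a rule that turns the nutrition field into compliant or non-compliant.

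**The concern.** The guideline item is defined by elapsed time, and the field meant to measure it holds none. A patient fasted at arrival and first fed at 20 hours, and one fasted for five days, can both be entered as nil per os. Two results are at stake: the compliance rate for this item, and its association with morbidity and mortality under the primary objective. A scoring rule written later cannot repair this, because the time will not have been collected.

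**Working it through.** The plan states no figure on this point, so there is none to reproduce. Step 1 compares the texts. Steps 2 to 4 illustrate the consequences, and their inputs are assumptions unless a source is given.

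**Step 1. Can the form recover the start time?** Imaging and endoscopic ultrasound (Section 7), ERCP (Section 9), necrosectomy and re-exploration (Section 10) and cholecystectomy (Section 12) all carry time bands. Nutrition carries none, and there is no later assessment and no reason for withholding feeding. The start time cannot be recovered. On the Section 7 usage, the patient fed at 20 hours was not fed on admission and would be entered as nil per os. That patient meets the Table 3 window if the feeding was oral (counting from admission), or the Table 4 window if it was enteral.

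**Step 2. Compliance rate.** Let C be the true share fed within the window and f the share of those who started after arrival. On a literal reading:

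measured compliance = C × (1 − f)

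| C | f = 10% | f = 25% | f = 50% | f = 75% |
|---|---|---|---|---|
| 21.4% | 19.3% | 16.1% | 10.7% | 5.3% |
| 50% | 45% | 37.5% | 25% | 12.5% |
| 80% | 72% | 60% | 40% | 20% |

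The 21.4% is borrowed from the Background, where it is the rate of early enteral nutrition in severe disease in one cited study. The other values of C, and all values of f, are assumed.

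If sites instead enter a route used later in the stay, let g be the share of patients not fed in the window whose later oral or enteral route is entered. Taking f = 0:

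measured compliance = C + (1 − C) × g

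With C = 50% and g from 10% to 75%, this runs from 50% + 5% = 55% to 50% + 37.5% = 87.5%. The error is then upward.

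**Step 3. Association, if patients fasted and then fed in time have the same risk as those fed from arrival.** Assume a true risk ratio of 2.0 for not being fed in time. On the literal reading:

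observed ratio = [C × f + 2 × (1 − C)] / [1 − C × (1 − f)]

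- C = 21.4%: 1.97 (f = 10%) to 1.83 (f = 75%)
- C = 50%: 1.91 to 1.57
- C = 80%: 1.71 to 1.25

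Check at C = 80%, f = 75%: (0.60 + 0.40) / (1 − 0.20) = 1.25. The attenuation is small where early feeding is rare and large where it is common.

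**Step 4. Association, if that subgroup has a different risk.** Assume 60% of patients are fed from arrival (mortality 9%), 24% are fasted and then fed in the window (mortality x), and 16% are not fed in the window (mortality 18%).

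- True contrast: 18% against (60 × 9% + 24 × x) / 84
- Measured contrast: (24 × x + 16 × 18%) / 40 against 9%

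| x | True contrast | True OR | Measured contrast | Measured OR |
|---|---|---|---|---|
| 9% | 18% v 9.0% | 2.22 | 12.6% v 9% | 1.46 |
| 15% | 18% v 10.7% | 1.83 | 16.2% v 9% | 1.96 |
| 18% | 18% v 11.6% | 1.68 | 18% v 9% | 2.22 |

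The two odds ratios cross at x of about 14%. At x = 14% they are 1.89 (true) and 1.87 (measured). Above that, the measured association is exaggerated.

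**The case against.** The strongest reply is that the form uses the phrase on admission loosely. Section 9 is headed as findings on admission, yet its ERCP bands run to 72 hours. Section 5 is headed as vital signs on admission, yet it holds ICU admission during the stay. Nasojejunal feeding and total parenteral nutrition, both offered as answers, suit an early inpatient plan better than a snapshot at the door. Several recommendations also concern route with no time limit (Table 1 item 16; Table 2 item 3; Table 3 recommendations 5 and 6), and the existing field does address those.

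Much of this stands. A reader might infer that patients fasted at arrival and fed in time will be coded nil per os, scored as non-compliant, and so dilute the association. The documents do not support that as fact: the phrase is undefined, no scoring rule is given, and dilution requires equal risk in that subgroup (Step 4). A reader might also infer a single window of 24 to 48 hours. There are two, one for oral and one for enteral feeding.

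The reply does not rescue the item. In Sections 5 and 9 the exceptions carry their own time label under a loose heading; in the nutrition field the phrase is part of the item's own label, as in Section 7. If sites do read it differently, the field is less reliable, and on either reading the start time is missing.

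**Conclusion.** The point holds in this form: the start of feeding is not recorded, so compliance with either tabled window cannot be determined. On a literal reading the compliance rate is understated; if sites enter a later route it could be overstated. The bias in the association with outcome is unknown in size and direction: toward no effect if misclassification is unrelated to outcome, possibly away from it if fasting at arrival tracks severity. The percentages and ratios above show what could happen and are not estimates for this study, because the documents give no start-time distribution and no risk by feeding time. One of eleven listed attitudes is affected. It should be corrected, because timing of nutrition is a gap the rationale itself names, but the other items are untouched.

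**What to change.** Beside the existing field, add one banded field in the form's own style: time from admission to first oral or enteral feeding (<24 h / 24-48 h / 48-72 h / >72 h / never / not recorded), with the route of that first feeding. State in the analysis plan that the item is scored separately against the oral 24-hour window and the enteral 48-hour window, and that the 24 hours are counted from admission, since Table 3 names no starting point. Keep the existing field for the route-only recommendations and define on admission in the form's instructions.

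Where the time cannot be obtained, or if data entry (01/03/2021 to 31/08/2021) is too far advanced to reopen records, report the item as route of nutrition on admission and not as compliance with early feeding.

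The cost is one CRF field, extra chart review at each centre, and some missing values; the documents do not show how often feeding times can be found in the records. One limit remains: Table 3 qualifies its recommendation by tolerance, which neither field captures, so the result should be described as feeding within the window and not as a judgement on each patient's care.

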#### **Study population**

All consecutive adult patients admitted to the participating surgical departments with a clinical and radiological diagnosis of biliary AP (with and without concomitant cholecystitis) between 01/01/2019 and 31/12/2020. Patient data will be retrospectively analyzed and demographic characteristics, comorbidity status, clinical and radiological findings, treatment strategies, 30-day morbidity and mortality will be evaluated.

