#### Inclusion criteria

Patients of both sexes,  $\geq 16$  years old, admitted to any of the participating surgical departments and/or

coMpliAnce with evideNce-based cliniCal guidelines in the managemenT of acute biliaRy pancreAtitis (MANCTRA-1). internal medicine or gastroenterology departments for biliary AP in 2019 and 2020.

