#### **Exclusion criteria**

Patients with AP of etiology other than gallstones; Pregnant patients.

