## Section 2 – Demographic Characteristics

- ! Year of hospital admission for acute biliary pancreatitis (2019 Vs. 2020)
- ! Patient age
- ! Sex (Female Vs. Male)
- ! Covid-19 status on admission (Negative/Positive/Untested)

- ! Previous episodes of biliary pancreatitis (Yes/No)
- ! Admitting speciality (HPB surgery/General Surgery/Internal Medicine/Gastroenterology)

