13. Management of biliary pancreatitis	
 
! Early ERCP/ES should be performed in gallstone-induced acute pancreatitis when complications of cholangitis or prolonged passage disorder of the biliary tract are suspected. (1A)
 
! To prevent the recurrence of gallstone-induced acute pancreatitis, cholecystectomy is recommended for cases where such surgery is possible. (1B)
 
! A cholecystectomy should be performed as soon as gallstone-induced acute pancreatitis has been resolved. (1B)
 

14. Management of abdominal compartment syndrome	
 
The sequential measurement of IAP is recommended for cases with excessive fluid infusion, high severity, renal and respiratory complications, and fluid accumulation in multiple areas as observed by CT, since the onset of ACS increases the mortality rate in such cases. (2C)
 
When there is persistent or recurrent IAPЯ12mmHg, conservative treatment (gastrointestinal decompression, intra-abdominal decompression, improvement of abdominal wall compliance, appropriate fluid infusion and circulation management) should be initiated. The goal should be to manage for IAPIO5mmHg. Surgical decompression should be considered only when internal treatment is not effective for patients with IAP>20mmHg and where the additional complication of organ failure is of concern. (2D)
 

15. Interventions for the local complications	! In principle, conservative treatment should first be performed for necrotizing pancreatitis. The best indication for intervention is applied to cases of infected pancreatic necrosis with suspected or confirmed infection

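### The CRF cannot identify patients who had already had a cholecystectomy, so they may be mixed into the 'No' group for early surgery

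*Combined protocol and SAP*

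**What the plan says.** **Who is eligible.** Study population admits patients "with and without concomitant cholecystitis) between 01/01/2019 and 31/12/2020". Inclusion criteria cover surgical departments and also "internal medicine or gastroenterology departments for biliary AP in 2019 and 2020". Exclusion criteria read, in full, "Patients with AP of etiology other than gallstones; Pregnant patients". None of these requires a gallbladder in place.

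**What the CRF records.** Section 12 has the codes "Yes-within 3 days/Yes-within 7 days/Yes-within 14 days/No-delayed cholecystectomy". The nearest history field is in Section 2: "Previous episodes of biliary pancreatitis (Yes/No"). No field in Sections 1 to 14 asks about earlier biliary surgery, and no completion rule says what to enter when cholecystectomy does not apply.

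**How the data are used.** The primary objective relates disregarded guideline items to poor outcomes, and Statistical analysis plans logistic regression of morbidity and mortality on clinical attitudes, among other variables. Secondary outcomes defines early definitive treatment as "cholecystectomy or ERCP with endoscopic sphincterotomy during the same hospital admission or within 2 weeks of discharge", and the matching compliance item is "Use of early definitive treatment strategies, including cholecystectomy and/or ERCP and sphincterotomy". The 2015 Japanese guidelines, reproduced among the guideline tables (item 13), say that "cholecystectomy is recommended for cases where such surgery is possible".

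**The concern.** Pancreatitis caused by a duct stone after an earlier cholecystectomy is still of gallstone origin, so on a plain reading such a patient is eligible. For that patient all four codes in Section 12 are untrue. The only one that is not a 'Yes' says that surgery was delayed.

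If sites use it, the 'No' group combines two kinds of patient: those whose surgery was withheld or postponed, and those for whom it was impossible. Only the first kind tells us anything about disregard of a guideline, which is the subject of the primary objective. No analysis of the collected data can separate them, because the distinguishing variable is not collected. Choledocholithiasis in CRF Section 9 cannot stand in for it, since patients with a gallbladder can have duct stones too.

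**Working it through.** The plan states no figure that depends on this field, so there is nothing to reproduce. The possible size follows from a simple mixture.

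**Inputs**
- *s*, the share of enrolled patients with an earlier cholecystectomy: not in the documents. Assumed 2%, 5%, 10% and 15%.
- *c*, the early cholecystectomy rate among patients who have a gallbladder: 25%, the same-admission rate that the Background quotes from a Canadian study. The Background also quotes 21.4% index-admission surgery from Singapore. A rate of 60% is added as an assumed high case. The Canadian figure is only a stand-in, because Section 12 counts surgery up to 14 days.
- All patients without a gallbladder are taken to be entered as 'No'.

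**1. Share of the 'No' group with no gallbladder:** *w* = s / [s + (1 − s)(1 − c)]. For s = 10% and c = 25%: 0.10 / (0.10 + 0.90 × 0.75) = 0.10 / 0.775 = 12.9%.

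**2. Recorded cholecystectomy rate:** c(1 − s), which is c × s below the rate in patients to whom the item applies. For the same case: 0.25 × 0.90 = 22.5%, a fall of 2.5 points.

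| s | w at c = 25% | Recorded rate at c = 25% | Fall (points) | w at c = 60% |
|---|---|---|---|---|
| 2% | 2.6% | 24.5% | 0.5 | 4.9% |
| 5% | 6.6% | 23.75% | 1.25 | 12% |
| 10% | 12.9% | 22.5% | 2.5 | 22% |
| 15% | 19.0% | 21.25% | 3.75 | 31% |

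The contamination grows with *c* because a high surgery rate leaves few true 'No' patients.

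**3. Regression on morbidity and mortality.** Before adjustment, the recorded risk in the 'No' group is (1 − w) × (risk in patients with a gallbladder and no early surgery) + w × (risk in patients with no gallbladder). At c = 25%, each point of difference between those two risks moves the group's risk by 0.026 to 0.19 points over the assumed range of *s*. The documents do not say which risk is higher, so the direction is unknown.

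**4. Composite early definitive treatment.** Let *d* be the composite rate in patients with a gallbladder and *e* the share of patients without one who have a recorded ERCP with sphincterotomy. The recorded rate is d(1 − s) + e × s, a change of s(e − d). With s = 10%:
- d = 25% (illustrative), e = 50%: 22.5% + 5% = 27.5%, a rise.
- d = 25%, e = 80%: 22.5% + 8% = 30.5%, a rise.
- d = 80% (the definitive treatment rate that the Background quotes from Sweden), e = 50%: 72% + 5% = 77%, a fall.

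The sign depends on whether *e* exceeds *d*. CRF Section 9 records ERCP only up to 72 hours, so a later qualifying procedure would be missed and *e* would be understated.

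**5. Readmission.** The recurrence code in CRF Section 14 is tied to waiting for interval cholecystectomy. Read literally, a patient without a gallbladder cannot meet it but stays in the denominator. The recurrence part of the rate is then multiplied by (1 − s), that is by 0.98, 0.95, 0.90 or 0.85.

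**The case against.** The strongest case on the other side has four parts.

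*These patients are not non-compliant in general.* A reader might infer from the missing code that all of them fail the compliance assessment. The documents do not support that. Both the outcome and the compliance item on early definitive treatment accept ERCP with sphincterotomy instead of surgery, and the plan's compliance list has no item on cholecystectomy alone. This stands. The problem is confined to the cholecystectomy recommendation, as it enters through the primary objective and the Section 12 variable, and to patients with no recorded ERCP on the composite.

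*Use of the 'No' code is inferred.* Sites might leave the field blank. This stands too, and 'may be coded' is as far as the text goes. A blank would not identify these patients either.

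*The readmission consequence is limited.* A reader might infer that leaving the gallbladder in place will look safer than it is. The plan compares readmission between 2019 and 2020 and describes no analysis of it by cholecystectomy status. If the share is similar in both years, the ratio of the recurrence rates is unchanged and their difference only shrinks. A site that stretches the Section 12 code may also stretch the recurrence code. What remains is dilution, conditional on a literal reading.

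*The subgroup is narrow.* The 'No' group also holds patients whose surgery is deferred in line with Table 1, item 22 (fluid collections), so the wider gap is the absence of a denominator for each guideline item. That is fair, but it does not remove this gap. Severity and some local complications are at least recorded in CRF Sections 4 and 10; previous cholecystectomy is recorded nowhere.

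**Conclusion.** The omission is real: eligible patients may have no gallbladder, the CRF cannot identify them, and Section 12 has no code that fits. If entered as 'No', they lower the recorded cholecystectomy rate and contaminate the comparison group for early surgery. That regression serves the primary objective, although the plan does not list its covariates, so the use of cholecystectomy timing as one of the clinical attitudes is a reasonable reading rather than a stated fact.

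The size is uncertain and probably modest. With surgery rates near those quoted from Canada and Singapore, the rate falls by 0.5 to 3.75 points and 2.6% to 19.0% of the 'No' group is affected, all on an assumed share of 2% to 15%. The larger figures, up to 31% of the 'No' group, need a surgery rate of about 60%, well above those two. The documents fix no direction for the composite rate or for the regression. Priority: minor.

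**What to change.** - Add a field to the CRF, for example in Section 2: cholecystectomy before this admission (Yes/No).
- Add a 'not applicable' code to Section 12.
- State in Statistical analysis that patients with an earlier cholecystectomy are left out of the cholecystectomy item and out of the denominator for recurrence while awaiting cholecystectomy, and that their early definitive treatment is scored on ERCP with sphincterotomy only.

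The cost is one field, one code and slightly smaller denominators. The data are collected retrospectively, so the history can be sought in the records already being consulted for each patient. No clinical care changes.
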